Phenotype and Metabolism: Phenotypic and metabolic changes in peripheral skeletal muscle of HF patients are well described (3,4,17-19). Phenotypic changes in fiber composition include reduced type I oxidative fibers (slow twitch) with increases in anaerobic type II (fast twitch) or hybrid fibers. Histomorphometric analyses also demonstrate decreased fiber sizes as well as reduced number and altered structure of mitochondria. Even though there is an increase in skeletal muscle fibers with anaerobic, fast twitch characteristics, fiber size and cross-sectional area are dramatically reduced, leading to a significant reduction in muscle force production in HF (20).

Related studies indicate metabolism of the skeletal muscle is altered in HF with shifts in aerobic/anaerobic enzyme distribution from slow oxidative towards fast oxidative and fast glycolytic isoforms (19), decreased levels of mitochondrial creatine kinase, as well as downregulation of the sarcoplasmic reticulum Ca^{2+} -ATPase 1 (SERCA-1) (21). While some have attributed HF skeletal muscle weakening and atrophy primarily to disuse, others assert the complex skeletal muscle changes in HF constitute a disease-related myopathy (22,23) that is then compounded by the effects of muscle disuse and deconditioning (24).

HF-related changes in the diaphragm strongly support the concept of intrinsic HF myopathy. HF is associated with diaphragmatic muscle changes consistent with increased activity (25), i.e., a shift from fast to

slow myosin isoforms, an increase in oxidative capacity and decreased glycolytic activity. Nonetheless, intrinsic performance remains deficient.

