Many atrogenes were linked to protein degradation, including polyubiquitin, Ub-fusion proteins, the Ub ligases atrogin-1/MAFbx which [name] discovered and characterized (39) as well as MuRF-1, multiple subunits of the 20S proteasome (and its 19S regulator) and cathepsin L. Many atrogenes were also down-regulated, including genes required for ATP production and late steps in glycolysis as well as transcripts for extracellular matrix proteins. A number of genes not previously implicated in muscle atrophy were dramatically up-regulated (lipin, metallothionein, AMP deaminase, RNA helicase related protein, TG-interacting factor) and several growth-related mRNAs were down-regulated (P311, JUN, IGF-1-BP5). Corroborating literature points to the importance of myostatin as a key gene regulating signal (40).

Our pilot data is similarly significant in demonstrating increased FoxO expression in human HF patients (see our pilot data). We also show key correlations between functional indices and FoxO, evidence which supports the premise that atrophy-associated transcriptional signaling patterns may be modified through exercise. Peak VO₂ (mLO₂•kg⁻¹•min⁻¹) correlates with FoxO ($r=-0.52$, $p<0.01$), MuRF-1 ($r=-0.42$, $p<0.05$), GLUL ($r=-0.36$, $p<0.5$), PGC-1 α ($r=0.49$, $p<0.05$), and IGFBP-5 ($r=0.60$, $p<0.01$). Additionally, GLUL correlates with strength and power ($r=-0.37$, $p<0.05$ and $r=-0.36$, $p<0.05$, respectively) and IGFBP-5 correlates with VE/VCO₂ slope ($r=-0.44$, $p<0.05$).

Growth regulating effects of IGF-1: Skeletal muscle studies in patients with advanced HF and cardiac cachexia have revealed involvement of IGF-1 in muscle catabolism/hypertrophy. Catabolic syndromes in chronic inflammation, sepsis or cancer show an altered state of the GH/IGF-1 axis most probably due to a peripheral IGF-1 deficiency, attributable in part to impaired IGF-1 response to GH (41,42) and possibly exacerbated by typical declines in IGF-1 with age. Proinflammatory cytokines such as TNF α uncouple the GH/IGF-1 axis through suppression of the GH receptor. In response, a state of GH resistance develops, commonly characterized by high GH and normal-to-low IGF-1, attributable in part to increased serum and local expression of proinflammatory cytokines such as IL-1 β and TNF α .

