Skeletal Muscle Analyses: Since the study's original funding, the VA Boston established its own laboratory facility for skeletal muscle research. [name], a VA investigator, and his laboratory staff will complete all skeletal muscle gene expression analyses. [name], an investigator from Beth Israel Deaconess Hospital, will no longer conduct PCR analyses but will remain on the study staff for his analytic insights. The analyses will center on genes previously defined as induced or suppressed in atrophying skeletal muscle (atrogenes) (35).

- **Atrogenes:** We will analyze gene sequences that code for skeletal muscle atrophy in the muscle biopsy specimens from HF patients and controls. As discussed above, these genes belong to a specific set of atrophy genes, aka atrogenes, which we previously characterized to be regulated in several models of skeletal muscle atrophy (35). We will particularly focus on FoxO, PSMA1 and GLUL, PGC1 and IGF-1 because our pilot studies defined significant differences in expression of these genes and correlations with muscle function in HF patients, but genes within all the following functional groups will also be analyzed:

1. **Protein degradation atrogenes:** atrogin-1/MAFbx, MuRF-1, Polyubiquitin (UbB UbC), proteasome subunits (PSMA1), cathepsin L.
2. **Growth factor pathways (molecular signaling related to growth):** PGC-1 α , FNDC5 (irisin), IGF-1, IGFBP5, FoxO1, FoxO3, myostatin, follistatin.
3. **Metabolic atrogenes,** lactate dehydrogenase, glutamine synthase.

- mRNA extraction and rtPCR: Total skeletal muscle mRNA will be extracted from muscle biopsies using Trizol reagent and well established protocols. Typically 5-10 μ g of total RNA is obtained from approximately half of a biopsy specimen. Samples will be stored in nuclease-free water at -80C. Total RNA will be converted to cDNA by reverse transcription using SuperScriptII reverse transcriptase (Stratagene) in standard reactions according to the manufacturer's recommendations.

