mRNA levels will be determined by real-time PCR using the Applied Biosystems® StepOne real-time PCR analyzer. Multiplexed amplification reactions will be performed using GAPDH as an endogenous control (GAPDH primers/VIC-labeled) using the TaqMan One Step PCR Master Mix reagents Kit (#4309169, Applied Biosystems). Probes/primers for the specific genes to be analyzed will be purchased directly from Applied Biosystems. The following amplification settings will be used: Stage 1 (reverse transcription): 48°C for 30 min; Stage 2 (denaturation): 95°C for 10 min and Stage 3 (PCR): 95°C for 15 sec and 60°C for 60 sec for 40 cycles. The Ct (Threshold cycle) values for each reaction will be transferred to a Microsoft Excel spreadsheet and calculation of relative gene expression will be performed from this data according to published algorithms (TaqMan Cytokine Gene Expression Plate 1 protocol, Applied Biosystems). All RNA samples will be analyzed in triplicate, with the mean value used in subsequent analyses.

Of note, in our pilot studies, biopsy data was initially evaluated on different 96-well plates to allow biopsy processing before the completion of the study; however, this was associated with high variability and poor precision. Analyses were then repeated with all of the biopsy samples on the same plate. This technique strengthened our analysis and revealed key differences and correlations between gene expression and function. In this proposed study, we shall prepare and store cDNA from the muscle biopsies in small groups as the biopsies are performed, and then perform rtPCR analyses batched by exercise arm in order to minimize plate-to-plate variation in the rtPCR data.

- **Microscopic Analyses:** [name] and a consulting microscopy technician will complete all light microscopic analyses at the Boston VA. [name] has an extensive track record of skeletal muscle phenotypic analysis. Both he and his laboratory staff will work directly with [name] to ensure the phenotypic assessments are completed in the most useful fashion. Given the controversial perspectives regarding the effects of disease vs.

deconditioning on skeletal muscle physiology and function, the attention to phenotypic assessments will be prioritized as a vital perspective relative to gene expression patterns and serologic assessments of inflammation.

- Muscle Tissue Histology and Morphometric Assessments

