General considerations: The analyses described below are of continuous outcome measures, primarily changes in function outcomes and gene expression and either continuous or categorical predictors. All analyses will be performed as general linear models. Potential confounders of each analysis will be outlined below and a 10% rule for evaluating confounders will be used, namely including a potential confounder if a 10% or greater change is seen in the main predictor effect. In all instances, outcome variables will be evaluated for violation of regression assumptions and transformation of these variables will be considered as a remedy if needed. Analyses will generally be performed with an intent-to-treat approach, with sensitivity analyses performed to assess the role of drop-outs on the results.

This grant examines a complex interplay of exercise regimens, gene expression and functional measures, resulting in a number of hypotheses that require testing. We are cognizant of the role of type I error in this and in interpreting results, focus will be placed on the overall results of these analyses and not on the results of individual tests. Thus, for example, significant relationships among gene expression outcomes and treatment categories as a whole will be considered as support for these hypotheses and isolated significant associations will not be unduly weighted in the interpretation of results.

Randomization will be generated using a SAS program based upon permuted random blocks of variable size to assure approximate balance over time and will be stratified by sex and statin use.

Validation of Study Measurements: At the start of the study, there will be two assessments of physical function battery. Intraclass correlations will be used to determine the relative repeatability of the various components of the battery. This information will be included in all manuscripts using these measures.

- *Aim 1. To assess differences in functional outcomes (peak VO₂, 1RM) relative to the training therapy:*

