a) *Aerobic vs. Strength vs. Aerobic-Strength regimens will be compared to one another b) Inspiratory Training will be compared to Aerobic-Strength:* In this aim, we compare the combined aerobic-strength training regimen to the single-therapy regimens of aerobic training and strength training, as well as the inspiratory training regimen. These comparisons will be made with changes in the functional outcomes (peak VO₂, 1RM) from baseline as the continuous outcome measures in separate models and training regimen as the categorical predictor in a general linear model, with the following factors considered as potential confounder variables: age, sex, and comorbidities. To limit the type I error rate, only the pre-planned comparisons of the combined aerobic-strength training to the other regimens will be considered. In addition, secondary analyses will consider the following aerobic, strength and inspiratory variables as outcome variables in similar analyses to those outlined above: 6MWT, sit-to-stand, and hand grip strength.

- **Aim 2. To assess gene expression and skeletal muscle perfusion in relation to the different training regimens:** In this aim, we examine the change from baseline to post-exercise regimen in the expression of proteolytic (FoxO and Ubiquitin) and anti-proteolysis (IGF-1 and PGC-1 α) genes as predictors of the change in functional outcomes (peak VO₂, 1RM) over the same period. Separate general linear models for each functional outcome will be performed with gene expression changes as the primary predictor and the following variables considered as potential confounders: age, sex, and comorbidities. As above, a 10% rule for introducing confounding variables and the transformation of outcome variables to deal with regression assumption violations will be considered.

Treatment regimens will also be categorized as those with and without direct skeletal muscle stimulation and this categorical variable will be considered as a predictor of a change in the expression of proteolytic and anti-proteolysis genes in general linear models in a similar fashion to that described above. In addition, similar general linear models will be used with changes in skeletal muscle perfusion as a continuous outcome and aerobic and inspiratory training vs. strength-only training as a categorical predictor with similar potential confounders as noted above.

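### Every muscle gene is scaled to GAPDH alone, with no stated check that GAPDH stays stable under training

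*Combined protocol and SAP*

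**What the plan says.** The section on mRNA extraction and rtPCR names one reference gene: "Multiplexed amplification reactions will be performed using GAPDH as an endogenous control". Threshold-cycle (Ct) values are kept for each reaction, and "calculation of relative gene expression will be performed from this data according to published algorithms".

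The Atrogenes list under Skeletal Muscle Analyses gives 16 targets, counting UbB and UbC separately: 6 protein-degradation genes, 8 growth-pathway genes and 2 metabolic genes ("lactate dehydrogenase, glutamine synthase").

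Three places treat muscle metabolism as changeable:
- The Background, on animal models of atrophy: "Many atrogenes were also down-regulated, including genes required for ATP production and late steps in glycolysis".
- Phenotype and Metabolism, on heart failure muscle: "shifts in aerobic/anaerobic enzyme distribution from slow oxidative towards fast oxidative and fast glycolytic isoforms".
- The Atrogenes list, which includes lactate dehydrogenase as a target.

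Aim 2 uses gene change in two ways. It is a predictor of change in peak VO₂ and 1RM. It is also an outcome: regimens are grouped by whether they stimulate skeletal muscle directly, and "this categorical variable will be considered as a predictor of a change in the expression of proteolytic and anti-proteolysis genes". On interpretation, the General considerations say that "significant relationships among gene expression outcomes and treatment categories as a whole will be considered as support for these hypotheses".

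**The concern.** Scaling to a reference gene works only if that gene does not respond to the treatment. With a single reference, a change in the reference and an opposite change in all the targets give the same scaled values. The scaled data alone cannot separate the two.

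A response that differs by arm is plausible here. The biopsy is taken from the vastus lateralis. Aerobic and combined training load that muscle; IMT does not. A training-related shift in GAPDH therefore need not be the same in every arm, and only a shift that differs between arms distorts the arm comparison.

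Reading the gene results as a whole is a reasonable guard against isolated chance findings. It gives no protection against an error that all the genes share. In the gene-to-function models, each patient's own GAPDH change would enter every gene predictor as common error.

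**Working it through.** **Calibration.** Sample size/Power states a detectable effect of 0.64 SD with 40 per group, 80% power and two-sided 5%.
- Normal approximation: (1.960 + 0.842) × √(2/40) = 0.626 SD.
- Noncentral t: 0.634 SD.

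Both agree with the stated 0.64, so the same t calculation is used below.

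**Algebra.** The published algorithms are not written out. I assume the usual form, with amplification close to doubling per cycle:

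relative expression = 2^−(Ct_target − Ct_GAPDH)

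If GAPDH Ct changes by s cycles, every scaled gene is multiplied by 2^s. A rise in Ct means less GAPDH, so all targets look higher; a fall has the inverse effect.

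| s (cycles) | Factor on all 16 genes |
|---|---|
| 0.25 | 1.19 |
| 0.33 | 1.26 |
| 0.50 | 1.41 |
| 0.60 | 1.52 |
| 1.00 | 2.00 |

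**Yardstick.** The pilot heart failure versus control means (Preliminary Data, Phase II), expressed in cycles:
- PSMA1: 4.4/3.5 = 1.26; log2 = 0.33
- UBB: 5.0/3.7 = 1.35; log2 = 0.43
- FoxO3: 6.5/4.3 = 1.51; log2 = 0.60

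These are cross-sectional differences, not training effects. They show only what size of difference the investigators have treated as meaningful.

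**Chance of a false arm difference.** Neither the SD of the change in scaled Ct nor the size of any GAPDH shift is given, so both are assumed. For a target that does not change at all, with a between-arm GAPDH difference s, the noncentral t has effect s/SD. Probability of a significant result with 40 per group, against a nominal 0.05:

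| Assumed SD | s = 0.25 | s = 0.50 | s = 1.00 |
|---|---|---|---|
| 0.75 | 0.31 | 0.84 | 1.00 |
| 1.0 | 0.20 | 0.60 | 0.99 |
| 1.5 | 0.11 | 0.31 | 0.84 |

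For IMT versus combined training, Table 5 plans 60 and 30 patients. Less 20% attrition, that is 48 and 24. At SD 1.0 and s = 0.50 the probability is 0.51.

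**Direction.** Suppose training truly changes the proteolytic genes by −d and the anti-proteolytic genes by +d on the log2 scale. A GAPDH shift s turns these into −d + s and +d + s. At s = d the first effect disappears and the second doubles. One group is masked and the other exaggerated.

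**Gene-to-function models.** For patient i and gene j, the observed log2 change is the true change plus g_i, the patient's own GAPDH Ct change. The same g_i enters every gene. If g_i is unrelated to function, it weakens each slope by var(true)/[var(true) + var(g)] and makes the predictors correlate with one another. If g_i is related to function, it adds an association of the same sign to every gene.

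**The case against.** The case against is substantial, and much of it stands.

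- **The biological premise is thin.** A reader might infer that the protocol itself says GAPDH changes with atrophy. It does not. It refers to late steps of glycolysis in animal models, and to enzyme distribution in heart failure muscle. It does not name GAPDH as an atrogene and gives no GAPDH data under training. The two statements do not even predict a direction: one describes falling gene expression, the other a move toward glycolytic isoforms.
- **A common shift cancels.** All arms train. A GAPDH change shared by all arms biases the before/after changes but drops out of the arm contrasts.
- **The hypothesis has directions.** A reader might infer that a GAPDH shift would produce exactly the pattern the plan counts as support. That goes too far. The legend to Figure 2 has exercise restraining FoxO and activating PGC-1α, whereas a GAPDH shift moves both groups the same way. This is partial protection only, because the General considerations set no rule about direction.
- **Some checking is possible.** A reader might infer that one reference leaves no way to detect a shift. GAPDH Ct is recorded in each multiplexed reaction, so it can be examined. However, the plan does not say it will be. The text also gives a typical RNA yield but no fixed input, without which raw Ct reflects the amount of RNA as well as GAPDH expression.
- **The magnitudes are hypothetical.** The false-positive probabilities rest on assumed shifts and SDs and are not evidence that a shift exists.

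What remains is the conditional point: a single reference, no stated check, and arms that load the biopsied muscle differently.

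**Conclusion.** The point holds as a conditional weakness that is cheap to remove. The supplied text names GAPDH as the only reference and states no stability check or alternative scaling. If GAPDH shifted differently between the leg-loading arms and IMT, all 16 genes would move by 2^s, and 0.33 to 0.60 cycles would match the pilot differences from PSMA1 to FoxO3. This rests on the usual Ct formula, near-doubling per cycle, and the outside knowledge that GAPDH encodes a metabolic enzyme.

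The documents do not support saying that the gene results will be biased, or by how much. The Aim 1 outcomes, peak VO₂ and 1RM, are unaffected. The priority is low, but the change should be made before PCR is run.

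**What to change.** 1. Prespecify at least one additional, non-glycolytic reference gene. Scale to the geometric mean of GAPDH and that gene, and keep GAPDH-only scaling as a sensitivity analysis. On the Ct scale the geometric mean of two references is the average of their Ct values, so a GAPDH shift s counts as s/2 if the other gene is stable. For example, 0.33 cycles becomes 0.165, a factor of 1.12 in place of 1.26.
2. Compare each patient's before/after change in GAPDH Ct between arms, with both samples on the same plate and a fixed RNA input. The paired change matters because PCR is to be batched by arm, so a comparison of Ct levels between arms would mix plate with arm.
3. Report the arm differences with confidence intervals and not only p-values. With 40 per group and an assumed SD of 1.0 cycle, the 95% half-width is 1.99 × √(2/40) = 0.45 cycles, so a non-significant result would not exclude a shift of 0.33. This is why the check should accompany the added reference and not replace it.
4. Do not use the target atrogenes as references. They were chosen because they change in atrophy, so scaling to them would repeat the fault.

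The cost is a few extra wells per plate on cDNA that the protocol already plans to store, plus slightly more analysis.

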Overall Study Protocol: 150 systolic HF patients will each undergo an initial clinical and mechanism-oriented assessment battery (involving 2-3 visits, depending on the site where they are enrolled) before and after being enrolled into one of 3 exercise training arms. The pre-/post- evaluations will include 1. a battery of physical function (aerobic and strength) evaluations, 2. serology, 3. muscle biopsy, and 4. DXA scan. The study population will be randomized into one of three 12-week exercise training arms (aerobic, combined aerobic-strength, and inspiratory muscle training [IMT]).

A SAS program will be written to randomly allocate patients to the exercise training arms (see statistics below), also balancing gender and statin-use (90) among these 3 exercise training groups. Enrollment into the exercise training groups will be on a rolling admission.

Notably, we used a 2-3 visit comprehensive assessment protocol as part of our pilot study. It was well tolerated by subjects with no complaints of excessive fatigue or inconvenience. We provided a gap of at least 15 minutes between each of the subparts, with leeway to allow extra time if that is requested by the subject or if it seemed indicated to the study staff. Furthermore, visits were arranged such that assessments requiring physical exertion were alternated with those which are physically non-taxing (e.g., questionnaires done at rest) to help

ensure that the overall protocol was well-tolerated. Heart rate and relative perceived exertion were also checked prior to each subpart of the assessment to confirm that the subject's baseline parameters had been restored before testing proceeded.

Exercise training will be 3X/week, for 60 minutes, over 12 weeks for each of the 3 exercise regimens through a combination of on-site and home-based exercise sessions. Phone calls will be completed weekly by trained exercise based research staff to check in with study patients, work to overcome barriers and modify exercise regimens. Each participant will exercise for a maximum of 12 weeks. If subjects miss training sessions due to intercurrent illness, travel or other reasons, the duration will not be extended as the proposed trial is based on an 'intention to treat' model.

The comprehensive 2-3-visit evaluation (including physical function plus muscle biopsy, and DXA) will be repeated at the end of the exercise training period.

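### The gene-expression assay is described as two incompatible workflows, and neither keeps a patient's baseline and post-training samples in the same run.

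*Combined protocol and SAP*

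**What the plan says.** The assay is set out under Skeletal Muscle Analyses, in the bullet on mRNA extraction and rtPCR and the text that follows it. Two descriptions stand there.

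- **Separate conversion.** "Total RNA will be converted to cDNA by reverse transcription using SuperScriptII reverse transcriptase". The closing paragraph, which explains what will change after the pilot, adds: "we shall prepare and store cDNA from the muscle biopsies in small groups as the biopsies are performed". It then plans to "perform rtPCR analyses batched by exercise arm in order to minimize plate-to-plate variation in the rtPCR data".
- **One-step assay.** Between those statements, the multiplexed reactions are to be run "using the TaqMan One Step PCR Master Mix reagents Kit". The thermal programme opens with "Stage 1 (reverse transcription): 48°C for 30 min". The text continues: "All RNA samples will be analyzed in triplicate".

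The timing comes from Overall Study Protocol: "The study population will be randomized into one of three 12-week exercise training arms", and "The comprehensive 2-3-visit evaluation (including physical function plus muscle biopsy, and DXA) will be repeated at the end of the exercise training period". Under Skeletal Muscle Biopsies, samples are held where they were collected and sent to the Boston laboratory in batches. Neither the shipping interval nor the size of a cDNA group is stated.

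Aim 2 in the statistical section uses each patient's change in expression as a predictor of change in peak VO₂ and 1RM, and also as an outcome compared between categories of regimen. The candidate covariates are age, sex and comorbidities. No batch or plate term is listed.

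**The concern.** If stored cDNA is the input, a reverse-transcription stage in the PCR run has nothing to do. If RNA is the input, the sentence about stored cDNA is wrong. The choice decides where run-to-run variation in reverse transcription enters the data.

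Aim 2 rests on a difference between two samples from one patient. A shift that both samples share cancels in that difference. If the samples are transcribed in separate runs, two independent shifts enter it instead. Plating stored cDNA together later does not help, because the variation is already in the material. Scaling to GAPDH removes only the part of the shift that affects all transcripts alike.

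The remainder adds variance where expression change is the outcome. Where it is the predictor, the remainder pulls the slope toward zero.

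**Working it through.** The plan states no figure on this point, so there is nothing to reproduce. Three checks follow.

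**1. Would a small cDNA group hold both samples of a patient?**

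Inputs: 150 patients, 100 in Pittsburgh and 50 in Boston (Table 5); attrition of 20%, so 80% to 100% have a second biopsy (Sample size/Power); training complete midway through year 4 (Project Time Line). Accrual is assumed to last 2.5 years if counted from year 2, or 3.5 years if counted from year 1.

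Biopsies in 12 weeks = N × (1 + retention) ÷ (years × 52) × 12.

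| Flow | Highest (2.5 years, 100% retained) | Lowest (3.5 years, 80% retained) |
|---|---|---|
| Both sites | 150 × 2 ÷ 130 × 12 = 27.7 | 150 × 1.8 ÷ 182 × 12 = 17.8 |
| Pittsburgh | 100 × 2 ÷ 130 × 12 = 18.5 | 100 × 1.8 ÷ 182 × 12 = 11.9 |
| Boston | 50 × 2 ÷ 130 × 12 = 9.2 | 50 × 1.8 ÷ 182 × 12 = 5.9 |

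A group formed from the pooled flow in order of arrival would need about 18 to 28 biopsies to span 12 weeks. With the 210 patients given under Sample size/Power, the range is 1.4 times larger, about 25 to 39. A small group would therefore normally split the pair. A split is not certain if Boston samples are handled alone (about 6 to 9 in 12 weeks) or if shipments are held for more than 12 weeks.

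**2. Could the one-step assay split the pair?**

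In triplicate, a 96-well plate holds 96 ÷ 3 = 32 samples for one gene, before controls.

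- Arm of 60: 60 × 2 × 3 = 360 wells, or 3.75 plates. With 48 completers: 288 wells, or 3.0 plates.
- Arm of 30: 30 × 2 × 3 = 180 wells, or 1.9 plates. With 24 completers: 144 wells, or 1.5 plates.

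Every arm needs more than one plate per gene. The only batching rule is by arm, so a pair can land on two plates.

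**3. What would the noise do?**

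Assume an SD of 1 cycle for a patient's change without batch error, and a residual transcript-specific batch SD of s cycles, independent at the two visits. Then Var(change) = 1 + 2s². With one predictor, the slope of functional change on measured expression change is multiplied by 1 ÷ (1 + 2s²).

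| s (assumed) | Variance of change | Slope factor |
|---|---|---|
| 0.2 | 1 + 0.08 = 1.08 | 0.93 |
| 0.3 | 1 + 0.18 = 1.18 | 0.85 |
| 0.5 | 1 + 0.50 = 1.50 | 0.67 |

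If both samples share a run, a shift common to the two cancels and the 2s² term disappears.

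**The case against.** The strongest reply is that the closing paragraph is the study-specific one and the one-step text is generic method description, so the laboratory will know what to do. That may be so. But it settles the contradiction in favour of stored cDNA, the workflow in which the pair is most likely to be separated.

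A reader might infer that every patient's two samples are reverse-transcribed in different batches. The documents do not say so. Group size and shipping interval are undefined, and the inference applies only to the stored-cDNA workflow. Under the one-step assay the pair shares a reverse-transcription run whenever it shares a plate run.

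A reader might also take the pilot's poor precision as a measure of this problem. The pilot text attributes it to the use of different PCR plates and does not isolate reverse transcription.

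The illustration has limits that stand. Both SDs are assumed. The reference SD of 1 cycle may already include biopsy-sampling and PCR error, so the factors are relative to the slope without batch error, not to the true biological slope. The formula also treats batch error as independent between patients. Patients in one batch share its shift, so part of it cancels between arms processed together. The 8% to 50% is therefore not the inflation of the regimen comparison. Cancellation would be incomplete, because Boston does not randomize to the combined arm.

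Nor does reverse-transcription batching by itself imply bias between arms. Under rolling, blocked enrolment such batches follow calendar time and mainly add noise. General considerations in the statistical section promises not to overweight isolated gene findings, but that does not correct attenuation.

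**Conclusion.** The contradiction is plain on the page: the section specifies both stored cDNA made in a separate step and a one-step assay on RNA. It is equally plain that no rule keeps a patient's two samples together under either workflow, although Aim 2 analyses their difference.

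Separate reverse transcription of the pair is the likely result of the stored-cDNA workflow as written. Separate plating is possible under the one-step workflow. The consequence is added noise in expression change and a weaker association with function, to the extent that transcript-specific batch variation survives GAPDH scaling.

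The size cannot be determined from the documents. The range of 8% to 50% more variance, with slopes at 93% to 67% of their value without this error, holds only for the assumed SDs and for one patient's change. Aim 1 does not use expression data and is unaffected. This is an inexpensive improvement that should be made before samples are converted.

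**What to change.** Name one workflow and delete the text that belongs to the other. Either of these would do:

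- **Two-step.** Hold extracted RNA at -80C, a storage condition the section already provides for. Once both samples of a patient exist, reverse-transcribe them in the same run with the same reagent lot, then place them on the same PCR plate.
- **One-step.** Run the kit on stored RNA with both samples of a patient in the same run, and remove the sentence on stored cDNA.

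Pairing need not add plates. A 32-sample plate holds 16 pairs per gene before controls, so 60 patients need 60 ÷ 16 = 3.75 plates and 30 patients need 1.9, the same as without pairing.

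The cost is a change in laboratory order and longer storage of RNA before conversion. No assays or staff are added.
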